Study Protocol and Statistical Analysis Plan

Study Title: Long Duration Activity and Metabolic Control After Spinal Cord Injury

NCT03139344

Document Version: 11/3/2022

Study Objectives

Skeletal muscle is the largest endocrine organ in the body, playing an indispensable role in glucose homeostasis. Spinal cord injury (SCI) prevents skeletal muscle from carrying out this important function. Dysregulation of glucose metabolism precipitates high rates of metabolic syndrome, diabetes, and other secondary health conditions (SHCs) of SCI. These SHCs exert a negative influence on health-related quality of life (HRQOL). New discoveries support that a low level of activity throughout the day offers a more effective metabolic stimulus than brief, episodic exercise bouts.

The **purpose** of this study is to translate this emerging concept to the population of individuals with SCI by using low-force, long-duration electrical muscle stimulation to subsidize daily activity levels. The **long-term goal** of this research is to develop a rehabilitation strategy to protect the musculoskeletal health, metabolic function, and health-related quality of life of people living with complete SCI.

Specific Aim 1: To compare acute changes in skeletal muscle gene regulation in individuals who receive a single session of low frequency (LF) or high frequency (HF) exercise.

Hypothesis 1: The expression of genes regulating skeletal muscle metabolism will support that HF and LF both initiate a shift toward an oxidative muscle phenotype.

Specific Aim 2: To compare changes in skeletal muscle gene regulation and systemic biomarkers of metabolic health in individuals with SCI who receive LF or HF for 6 months.

Hypothesis 2: LF and HF will both yield gene expression changes indicating a shift toward a slow-oxidative muscle phenotype.

Hypothesis 3: LF training will yield systemic biomarker changes indicating improved glucose homeostasis and reduced systemic inflammation.

Specific Aim 3: To measure subject-reported HRQOL using the PROMIS survey metric.

Hypothesis 4: LF training will yield improved self-reported QOL via PROMIS physical and mental health scales.

Design

Population: Individuals with motor-complete spinal cord injury (SCI) (AIS A – B), 21 to 60 years of age.

Exclusion Criteria: Pressure ulcers, chronic infection, lower extremity muscle contractures, deep vein thrombosis, bleeding disorder, recent limb fractures, any comorbid disease known to affect bone metabolism (such as parathyroid dysfunction), pregnancy, anti-osteoporosis medications, Vitamin D supplements, Metformin or other medications for diabetes

Enrollment: Non-random assignment

Study Arm 1: Acute gene regulation in response to a single session of low frequency electrically induced exercise

Study Arm 2: Acute gene regulation in response to a single session of high frequency electrically induced exercise

Study Arm 3: Adaptations in gene regulation, systemic metabolic markers, and patient-report metrics in response to training with low frequency electrically induced exercise

Study Arm 4: Adaptations in gene regulation in response to training with high frequency electrically induced exercise

Study Arm 5: Comparator participants will undergo selected outcome measures to provide comparison values for Experimental arms.

Methods

Baseline Characteristics: Participants will provide information on age, sex, race, ethnicity, and level of SCI (quadriplegia, paraplegia)

Study Arms 1 and 2: Participants will undergo unilateral vastus lateralis skeletal muscle biopsy: they will be positioned in supine, the skin over the biopsy site will be sterilized, up to 3 mL of 1% lidocaine will be injected locally, and a 1/8th inch incision will be made with a scalpel. The biopsy needle will then be inserted and four cores of muscle (~ 20 mg) will be obtained from four passes of the needle through the same puncture site. The incision site will be closed with steri-strips or a butterfly bandage and the subject will be told not to perform electrical muscle stimulation or wet the area for 48 hours. Muscle specimens will be immediately processed for microarray analysis. Participants will then undergo a single session of electrically-induced low frequency (Arm 1) or high frequency (Arm 2) exercise to the quadriceps and hamstrings muscles of the non-biopsied limb. Stimulating electrodes will be placed over the quadriceps and hamstrings muscles, and electrical stimulation will be given to induce an isometric closed kinetic chain knee extension moment. Participants will rest for 3 hours and then the vastus lateralis biopsy procedure will be repeated on the limb that performed electrically-induced exercise.

Study Arm 3: Participants will complete a baseline assessment including the biopsy procedure described above, completion of the PROMIS self-reported quality of life survey, and venipuncture. Venous blood will be collected into vacutainer tubes with anticoagulant for glucose, kept on ice in dark conditions. The

blood will be centrifuged and analyzed with a blood auto-analyzer. After two weeks, participants will begin low frequency electrically induced exercise training. They will perform electrically induced exercise as described above for 6 months. At the conclusion of training, participants will undergo repeat biopsy, PROMIS survey, and venipuncture.

Study Arm 4: Participants will complete a baseline muscle biopsy assessment using the procedure described above. After two weeks, participants will begin high frequency electrically induced exercise training. They will perform electrically induced exercise as described above for 6 months. At the conclusion of training, participants will undergo repeat biopsy.

Study Arm 5: Comparator participants will complete the PROMIS self-reported quality of life survey.

Outcome Measures: Microarray will be used to measure mRNA transcription levels for genes that regulate cellular adaptation to exercise (peroxisome proliferator-activated receptor gamma coactivator alpha – PGC1-alpha), muscle oxidative metabolism (pyruvate dehydrogenase kinase – PDK4, actin binding Rho activating protein – ABRA, and nuclear receptor subfamily 4 group A member 3 – NR4A3), and muscle fiber type (myosin heavy chain 6 – MYH6, myosin light chain 3 – MYL3, myosin heavy chain 7 – MYH7, actin 3 – ACTN3).

Standard clinical assays will be used to measure levels of serum biomarkers for metabolic control (fasting insulin, fasting glucose, fasting glucose-insulin ratio, fasting hemoglobin A1c) and systemic inflammation (c-reactive protein – CRP).

For the PROMIS participant-report metric of health-related quality of life, raw scores will be used to calculate the physical health t-scale and the mental health t-scale.

Statistical Analysis Plan

Gene mRNA transcript levels will be expressed as Log_2 intensity (arbitrary units). Each blood biomarker will be expressed as its commonly-used clinical unit of measure (eg. mg/dL). PROMIS physical and mental health scores will be expressed as t-scores, which are anchored to the U.S. population mean (50) and standard deviation (10).

Change over time for each gene-related outcome measure will be assessed via one-way ANOVA. For study Arms 1 and 2, gene expression levels from the baseline biopsy will be contrasted to the 3 hour post-exercise biopsy. For study Arms 3 and 4, gene expression levels from the pre-training biopsy will be contrasted to the post-training biopsy.

For study Arm 3, change over time in pre-training and post-training values for systemic biomarkers and for PROMIS scores will be assessed via 2-sided t-tests.

Pre-training values for PROMIS scores in study Arm 3 will be contrasted with the comparator cohort (study Arm 5) via 2-sided t-tests.

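### Arms 1 and 2: the two biopsies always come from opposite limbs and the rule for choosing the limb is not stated, so a systematic limb difference could not be told apart from an exercise effect

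*Combined protocol and SAP*

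**What the plan says.** Under Methods, Study Arms 1 and 2, the first procedure is one-sided: "Participants will undergo unilateral vastus lateralis skeletal muscle biopsy". The single stimulation session then goes to the other leg: "exercise to the quadriceps and hamstrings muscles of the non-biopsied limb". After three hours' rest, "the vastus lateralis biopsy procedure will be repeated on the limb that performed electrically-induced exercise". The baseline and 3-hour specimens therefore come from opposite limbs in every participant.

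The Statistical Analysis Plan treats the two specimens as a time contrast: "Change over time for each gene-related outcome measure will be assessed via one-way ANOVA", and "For study Arms 1 and 2, gene expression levels from the baseline biopsy will be contrasted to the 3 hour post-exercise biopsy". It names no limb or side term and does not mention pairing.

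The Methods text specifies the local anaesthetic, the incision and the number of needle passes, but not how the first limb is picked. The Design section has the line "Enrollment: Non-random assignment", which concerns allocation to arms. For Arms 3 and 4 the document does not say which limb is re-biopsied, so this point is confined to Arms 1 and 2.

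**The concern.** Moving to the other limb for the second biopsy is a reasonable way to keep the local effect of the first needle out of the second specimen. The price is that limb and exercise change together. There is no baseline specimen from the exercised limb and no 3-hour specimen from the unexercised one, so within a person the two are fully confounded. Only the way limbs are chosen across participants can protect the mean contrast, and the plan is silent on that.

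Hypothesis 1 expects both stimulation frequencies to start a shift toward an oxidative phenotype, so it is judged on each arm's own pre/post change. If both arms used the same non-random limb rule and the limbs differed on average, the same spurious shift would appear in both arms and would look like agreement between them. The fibre-type genes among the outcomes would also carry any standing difference in fibre composition between limbs.

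**Working it through.** **Inputs from the document.** Opposite-limb sampling; a pre/post contrast on the log2 intensity scale; no side term. No sample size, alpha, SD or limb-to-limb difference is given for the gene outcomes, so there is no planned figure to reproduce.

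**Inputs assumed for illustration.** n = 10; SD of the within-person log2 difference 0.5; two-sided 5% paired t-test; true exercise effect zero; mean difference between side A and side B, δ = 0.1, 0.2 or 0.3 log2 units; p = share of participants exercised on side A.

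**Step 1: bias.** A participant exercised on side A contributes +δ to the post-minus-baseline difference, and one exercised on side B contributes −δ. The expected bias is pδ − (1 − p)δ = (2p − 1)δ. This is δ at p = 1, 0.5δ at p = 0.75 and 0 at p = 0.5.

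**Step 2: false-positive rate, same side in everyone (p = 1).** The noncentrality is δ√n / SD. With √10 = 3.162 this is 0.632, 1.265 and 1.897. Against the critical value 2.262 (9 df), the noncentral t gives 0.088, 0.205 and 0.396.

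**Step 3: other splits.** These were simulated under the same assumptions, with each participant's side drawn with probability p.

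| Share exercised on side A | δ = 0.1 | δ = 0.2 | δ = 0.3 |
|---|---|---|---|
| 100% (worst case) | 0.088 | 0.205 | 0.396 |
| 75% | 0.059 | 0.085 | 0.124 |
| 50%, chosen at random | 0.050 | 0.050 | 0.051 |

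With an exact 5/5 split and a side term, the simulated rate is 0.050 at all three shifts. With 5/5 and no side term the test is conservative (0.046, 0.036, 0.024), because the side difference inflates the SD. This is a reason to fit the term.

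**Step 4: sample size.** At p = 1, n = 6 gives 0.069, 0.127 and 0.224, and n = 20 gives 0.136, 0.397 and 0.721. The rate rises with n because the problem is bias, which more participants do not cure.

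**Step 5: low versus high frequency.** The bias in the between-arm difference is (2p₁ − 1)δ − (2p₂ − 1)δ = 2(p₁ − p₂)δ, which is zero when both arms use the same limb rule.

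**Step 6: limb differences with mean zero.** If these vary between persons with an SD of r times the remaining SD, the paired sample size needed grows by 1 + r²: 1.06, 1.25 and 2.0 for r = 0.25, 0.5 and 1. That is lost precision, not bias.

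**The case against.** A reader might infer that one side is always exercised, or that the line on non-random assignment covers the limb. The document supports neither: that line concerns arms, and on limb choice the text says nothing. Nor does it suggest that operators keep a better-responding limb for exercise, since no pre-test of limb response is described. Bias needs two things together, a systematic choice and a mean expression difference in that direction, and neither is shown. Entry is limited to motor-complete injury, which weakens voluntary dominance as a source of asymmetry. The exclusions for contracture, recent fracture, thrombosis and pressure ulcers remove some other sources. This all stands, and it is why the point concerns an unprotected contrast and not a demonstrated bias.

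It is also fair that the 9%, 21% and 40% figures are a worst case under a test that the plan does not clearly specify. If the one-way ANOVA were run unpaired, with the same SD of the difference and the same side in everyone, the rates would be about 2%, 7% and 19% at a within-person correlation of 0.5, and about 5%, 13% and 30% at 0.3. These are lower because ignoring the pairing makes the test conservative. The bias in the estimate is unchanged.

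Finally, one may say that writing down the rule would be enough. It would not: a stated but one-sided rule leaves the confounding in place, and a side term cannot then be estimated, because side and time coincide.

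**Conclusion.** The point holds in a conditional form. In Arms 1 and 2 limb and exercise are fully confounded within each participant, the limb-selection rule is not stated, and the analysis has no limb term. Unless limb choice is random or counterbalanced, a systematic limb difference cannot be separated from exercise in each arm's own pre/post contrast.

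The actual size cannot be computed from the document. The illustrative false-positive rates run from the nominal 5% with random sides to 40% for a 0.3 log2 shift with one side always exercised. They rest on an assumed n, SD and shift and on a paired t-test. They should not be read as the trial's expected error rate, and they do not carry over to the low-versus-high-frequency comparison if the arms share a limb rule. The change is worth making because it is cheap and removes a possible bias from the contrast behind Hypothesis 1.

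**What to change.** Keep the two-limb design. Where both limbs are eligible, randomise right or left for the baseline biopsy, balanced within Arm 1 and within Arm 2. Record the side of every specimen. Analyse the within-person differences in a paired model with side as a term: difference = exercise effect + side effect × (±1 for right or left exercised).

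The cost is an allocation list and one degree of freedom (9 to 8 in the example), with no extra biopsy or visit. If the specimens are already collected, state the rule that was used, report the side of each biopsy and, if sides varied, fit side in the paired model.

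The limits should be stated. Randomising deals with any limb-selection bias, including choice of a better or worse limb, whereas a side term alone removes only a common right-left difference. Person-specific limb differences remain as noise. Time and the first biopsy procedure remain confounded with exercise, because no unexercised 3-hour specimen is taken.

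### The gene analysis names an unqualified one-way ANOVA for two biopsies from the same participant; taken literally it ignores the pairing and uses the wrong standard error

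*Combined protocol and SAP*

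**What the plan says.** The gene analysis in the Statistical Analysis Plan is one sentence naming the test and two naming the contrasts:

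- Test: "Change over time for each gene-related outcome measure will be assessed via one-way ANOVA".
- Acute arms: "For study Arms 1 and 2, gene expression levels from the baseline biopsy will be contrasted to the 3 hour post-exercise biopsy".
- Training arms: "For study Arms 3 and 4, gene expression levels from the pre-training biopsy will be contrasted to the post-training biopsy".

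The Methods section shows that both biopsies in each contrast come from one person. In Arms 1 and 2 the first biopsy is taken from one leg, the stimulation is "exercise to the quadriceps and hamstrings muscles of the non-biopsied limb", and after the rest period "the vastus lateralis biopsy procedure will be repeated on the limb that performed electrically-induced exercise". The pair is therefore same person, opposite limb. In Arm 3, "At the conclusion of training, participants will undergo repeat biopsy, PROMIS survey, and venipuncture"; Arm 4 likewise has a biopsy before and after training.

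The other tests in the plan are described as follows. For Arm 3, "change over time in pre-training and post-training values for systemic biomarkers and for PROMIS scores will be assessed via 2-sided t-tests". For the comparison with the comparator cohort, "Pre-training values for PROMIS scores in study Arm 3 will be contrasted with the comparator cohort (study Arm 5) via 2-sided t-tests".

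Nowhere do the documents mention pairing, repeated measures, a within-participant factor or a participant term.

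**The concern.** One-way ANOVA has a default meaning: independent groups, with the error term taken from the spread between individuals within each group. With two levels it is the unpaired t-test. Applied to two biopsies from one person, it leaves the stable differences between people in the error term, although they cancel out of the change being tested.

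The rest of the plan does not settle which test is meant. It uses the same unqualified two-sided t-test for a within-person comparison (Arm 3 before and after training) and, in the next sentence, for a comparison of two different cohorts (Arm 3 against Arm 5). Pairing is simply not marked.

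The sentence governs all eight genes named under Outcome Measures, in four of the five arms, and so carries Hypotheses 1 and 2. If ρ is more than small, following it literally discards information from participants who each undergo two muscle biopsies. Whatever ρ is, two analysts could run different tests on the same data, get different p-values, and both claim to have followed the plan.

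**Working it through.** **Inputs.** From the documents: the test name, two time points per contrast, the same participant at both, and a continuous log2 outcome. Not in the documents, so assumed: n participants per arm; d, the mean change in units of the single-occasion SD; ρ, the within-person correlation; two-sided alpha of 5%; bivariate normality; and equal SD σ at both times unless stated otherwise. The plan has no power or sample-size figure to reproduce.

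**Step 1: what the named test is.** On a generated data set, the two-level one-way ANOVA F and the squared unpaired t were both 0.7336; the squared paired t was 0.4692. On a second set (n = 10), one-way ANOVA and unpaired t both gave p = 0.9461, while repeated-measures ANOVA and paired t both gave p = 0.8658.

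**Step 2: standard error.** The variance of the mean change is

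- as the unpaired test takes it: 2σ²/n
- in truth: 2σ²(1−ρ)/n

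The ratio of standard errors is 1/√(1−ρ):

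- ρ = 0.1: 1/√0.9 = 1.05
- ρ = 0.3: 1/√0.7 = 1.20
- ρ = 0.5: 1/√0.5 = 1.41

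With unequal SDs the ratio is √[(σ₁²+σ₂²)/(σ₁²+σ₂²−2ρσ₁σ₂)]. For SDs of 1 and 2 at ρ = 0.5 it is √[5/(5−2)] = 1.29. The factor is smaller but still exceeds 1 for every ρ > 0.

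**Step 3: type I error of the literal test** at n = 10, nominal 5%: 4.0% at ρ = 0.1, 2.3% at 0.3, 0.95% at 0.5.

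**Step 4: power.** For the paired test, use the noncentral t with n−1 df and noncentrality d/√(2(1−ρ)/n). At n = 10, d = 0.8, ρ = 0.5 this is 0.8/√0.1 = 2.53 on 9 df, giving 61.6%. For the unpaired test on correlated pairs, the mean difference is N(d, 2(1−ρ)/n) and the pooled variance is [(1+ρ)C₁+(1−ρ)C₂]/(2(n−1)), in units of σ², with C₁ and C₂ independent chi-square on n−1 df. It is referred to t on 2n−2 df, and power is obtained by numerical integration.

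Power at n = 10, d = 0.8:

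| ρ | Unpaired (literal) | Paired |
|---|---|---|
| 0 | 39.5% | 35.9% |
| 0.1 | 39.0% | 39.2% |
| 0.3 | 38.0% | 48.0% |
| 0.5 | 36.7% | 61.6% |

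Simulation with 200,000 trials at ρ = 0.5 gave 36.7% and 61.6%.

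**Step 5: where pairing starts to pay.** The unpaired test has 2n−2 df against n−1, so at very small ρ it is slightly more powerful. Break-even ρ:

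| d | n = 5 | n = 10 | n = 20 |
|---|---|---|---|
| 0.5 | 0.086 | 0.059 | 0.040 |
| 0.8 | 0.150 | 0.096 | 0.065 |
| 1.2 | 0.224 | 0.141 | 0.095 |
| 1.5 | 0.272 | 0.173 | 0.118 |

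Outside this grid it can be larger: about 0.40 at n = 4, d = 2. An example below break-even is n = 5, d = 0.8, ρ = 0.1, with power 19.1% unpaired against 17.9% paired.

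**The case against.** The strongest reply is that the sponsor probably meant the right thing. The sentence is about change across time, the next two sentences set each arm's later biopsy against its earlier one, and one-way ANOVA may be shorthand for a one-way repeated-measures ANOVA, which with two time points is the paired t-test. This stands as a reading of intent. It does not supply the missing specification: a question about change does not name an error term, and the test as named has an ordinary meaning that is unpaired.

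Second, for ρ > 0 the error is conservative and does not manufacture findings. That stands.

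Third, the loss of power is not established. Nothing in the documents fixes n, effect size or ρ, and ρ may be lower in Arms 1 and 2, which carry Hypothesis 1, because the biopsies come from opposite limbs. That also stands, and it limits what can be said about size. It does not rescue the wording, because the literal test holds its nominal error rate only at ρ = 0.

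Fourth, the factor 1/√(1−ρ) requires equal variances, and the paired test's exact error rate requires normally distributed differences, which matters with very few participants. Both caveats are right; neither changes the direction.

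Finally, the Arm 3 t-tests are naturally read as paired. Agreed: the term t-test has no single default form, so the gap there is one of clarity only.

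**Conclusion.** The concern holds. Followed as written, the gene analysis is an unpaired test on paired data, and its standard error is wrong whenever ρ differs from zero: too large on average for positive ρ, too small for negative ρ. Under the Step 2 and Step 3 assumptions, a correlation of 0.3 inflates the standard error by about 20% and takes the true type I error from 5% to 2.3% at n = 10.

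The cost in power for Hypotheses 1 and 2 is conditional. In the illustrative case it is nothing or a slight gain up to ρ of about 0.1, about 10 points at ρ = 0.3 (48.0 − 38.0) and about 25 points at ρ = 0.5 (61.6 − 36.7). The actual loss cannot be calculated from the documents. Confidence is moderate because the sponsor's intention is unresolved; that the text specifies no pairing is not in doubt.

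**What to change.** Replace the gene-analysis sentence with, for example:

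> For each gene outcome, the difference between the two biopsies will be tested within each of Arms 1 to 4 by a paired t-test on the within-participant difference in log2 intensity (equivalently, a one-way repeated-measures ANOVA with time as the within-participant factor).

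This wording also makes explicit that each arm is tested separately, which the plan does not state in so many words; the sponsor should confirm it. For clarity, the Arm 3 before-and-after tests could be called paired and the Arm 3 against Arm 5 test two-sample.

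**Cost.** Wording only, with no new data; if repeated measures was always intended, nothing but clarity changes. Two real costs should be acknowledged:

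- If ρ is in fact zero, pairing gives up some power: 3.6 points at n = 10, d = 0.8 (39.5% to 35.9%), 7.7 points at n = 5, d = 1.2 (38.6% to 30.9%), 10.9 points at n = 5, d = 1.5 (54.9% to 44.0%), and about 17 points at n = 4, d = 2 (65.7% to 49.0%). This matters most for the opposite-limb biopsies in Arms 1 and 2.
- A paired test uses complete pairs only. With six months of training in Arms 3 and 4 and no missing-data rule in the plan, a participant without a second biopsy drops out of the analysis. A mixed model with a participant term is an alternative that keeps the single observations.

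In return, with normally distributed differences, the test holds its nominal error rate at any ρ.

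### Does the plan need a multiplicity rule before the gene, biomarker and PROMIS results can be read against Hypotheses 1–4?

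*Combined protocol and SAP*

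**What the plan says.** Study Objectives states four hypotheses. Hypothesis 1, on a single session (Arms 1 and 2), reads "The expression of genes regulating skeletal muscle metabolism will support that HF and LF both initiate a shift toward an oxidative muscle phenotype". Hypothesis 2, on six months of training (Arms 3 and 4), reads "LF and HF will both yield gene expression changes indicating a shift toward a slow-oxidative muscle phenotype". Hypotheses 3 and 4 concern low-frequency training only: "LF training will yield systemic biomarker changes indicating improved glucose homeostasis and reduced systemic inflammation" and "LF training will yield improved self-reported QOL via PROMIS physical and mental health scales".

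Methods, Outcome Measures, names eight genes: one for adaptation to exercise (PGC1-alpha), three for oxidative metabolism (PDK4, ABRA, NR4A3) and four for fibre type (MYH6, MYL3, MYH7, ACTN3). It also names four metabolic markers ("fasting insulin, fasting glucose, fasting glucose-insulin ratio, fasting hemoglobin A1c"), CRP, and two PROMIS scales.

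The Statistical Analysis Plan says "Change over time for each gene-related outcome measure will be assessed via one-way ANOVA", with a before–after contrast for Arms 1 and 2 and another for Arms 3 and 4. Arm 3's biomarkers and PROMIS scores get two-sided t-tests. The document states no significance level, adjustment, direction per gene, sample size, or rule for combining genes, markers or arms into a verdict on a hypothesis.

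**The concern.** Each of Hypotheses 1 and 2 is a joint claim about two arms. If one frequency works and the other does nothing, the claim is false, and it is made in error whenever the inactive arm happens to meet whatever standard of support is used. With eight genes tested separately and no standard written down, a lenient standard (any one significant gene) would make that error fairly common. A strict one would make it rare. An unwritten standard can also drift toward the one that suits the data.

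Hypothesis 3 has a similar exposure. If CRP truly improves and no metabolic marker does, one chance result among four markers could complete the claim. A reader would reasonably ask for a stated level, a multiplicity method and a support rule.

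**Working it through.** The plan gives no error rate to reproduce, so the check asks how large the error is under each plausible reading.

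**Inputs from the document.** Eight genes in each of four arms, five biomarkers, two PROMIS scales. Tests bearing on the hypotheses, if each arm is analysed separately: 8 × 4 + 5 + 2 = 39. The two Arm 3 versus Arm 5 PROMIS contrasts, which no hypothesis uses, make 41.

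**Assumptions.** A 5% two-sided level, so 0.025 per gene in the favourable direction; exact test size; independent genes unless stated; the working arm always detected.

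**Chance that an inactive arm meets the standard, favourable direction, no adjustment:**

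- Any one of eight: 1 − 0.975^8 = 0.183.
- Any one of the four adaptation and metabolism genes: 1 − 0.975^4 = 0.096.
- At least two of eight: 1 − 0.975^8 − 8 × 0.025 × 0.975^7 = 0.016.
- At least two of four: 1 − 0.975^4 − 4 × 0.025 × 0.975^3 = 0.0036.

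With a common correlation of 0.5 between genes (simulation), these become 12.5%, 7.8%, 4.3% and 1.7%.

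**If direction is ignored** (0.05 per gene): any of eight is 1 − 0.95^8 = 0.337; at least two of eight is 0.057 (0.086 at correlation 0.5).

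**Power in the working arm.** The joint error is the inactive-arm chance times that power. For any one of eight: 0.183 × 0.8 = 0.147, and 0.183 × 0.5 = 0.092.

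**Unpaired analysis.** If the one-way ANOVA ignores that both biopsies come from the same person, the test is conservative. At an assumed within-person correlation of 0.5 and 6–20 people per arm, any one of eight favourable falls to about 3–5%.

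**Hypotheses 3 and 4.** With CRP truly improved, any one of four metabolic markers favourable is 1 − 0.975^4 = 0.096, or 7.8% at correlation 0.5. Independence cannot hold here, because the glucose-insulin ratio is computed from two of the other markers. If CRP is the null part, the error is at most 2.5%. For PROMIS, requiring both scales also holds it to at most 2.5%; accepting either gives 1 − 0.975^2 = 0.049 when neither scale improves.

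**What adjustment would buy.** Applying Benjamini-Hochberg to eight genes per arm takes the one-gene standard from 18.3% to 2.6% when every gene in the inactive arm is null. That is not a guarantee. If some genes there truly move unfavourably (mean shift of −4 standard errors), their rejections loosen the threshold for the rest. Simulation then gives a false favourable gene in 5.4% of cases with two such genes and 6.0% with four.

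**What it would cost.** Simulated paired t-tests, 6–20 people per arm (assumed), independent genes, 80% unadjusted power per true gene:

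- One true gene of eight: 80% falls to 35% (n = 6), 39% (n = 8), 45% (n = 12) and 48% (n = 20).
- Four true genes, at least two detected: unadjusted 1 − 0.2^4 − 4 × 0.8 × 0.2^3 = 0.973; adjusted 70–82% per arm.
- Both arms must pass. Treating them as independent, 0.973^2 = 0.95 falls to between 0.70^2 = 0.49 and 0.82^2 = 0.67.

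**The case for a change.** The strongest case for a change is that the document states four directional hypotheses and never calls them exploratory. It leaves the level, the directions and the support rule unwritten, and nothing in it excludes the lenient reading. For the fibre-type genes especially, a favourable change is not defined gene by gene, so the 34% figure cannot be ruled out on the text alone. The wording would be cheap to add and needs no new data.

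Much of this stands. The omissions are real, not a product of redaction or text extraction, and the arithmetic behind 18% and 34% is correct. A report that rested either joint claim on one significant gene of eight in one of the arms would deserve little weight.

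What does not stand is the step from there to a defective plan. The percentages describe rules a reader might supply, not a rule the plan adopts. The documents also do not show that a rule will be picked after the data are seen. The gene list is fixed in advance, so a reader can see how many of the eight moved and which way. As for the remedy, a short instruction to adjust would leave open the choices that matter: which genes form the family, how many must change, in which direction, and whether one PROMIS scale suffices.

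**Conclusion.** No change to the plan follows. Hypothesis 1 speaks of genes and Hypothesis 2 of changes, both toward an oxidative phenotype, so the natural reading is a pattern of several genes moving the expected way in each arm. On that reading, with two or more favourable genes, the false joint claim runs at 0.4–1.6% with independent genes and 1.7–4.3% at correlation 0.5. It is below 5% without adjustment. The 18% figure needs one gene to suffice, and the 34% figure also needs direction to be disregarded. Hypothesis 3 already asks for both metabolic and inflammatory improvement, which leaves about 8–10% in one configuration and at most 2.5% in the other. Hypothesis 4 names both scales, which holds its error to at most 2.5%.

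Formal adjustment is a trade-off on which reasonable statisticians would differ. It does not reliably hold the one-gene standard near 2.6%, and it would cost substantial power in a mechanistic study if arms are as small as assumed here.

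The conclusion rests on a conventional 5% two-sided level, on analysts judging direction from the known role of each gene, and on 6–20 people per arm for the cost figures. The document states none of these. If two genes counted regardless of direction, the error would be 6–9% over eight genes, so the directional reading matters.
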